## Glossary of Abbreviations

RCoA	Royal College of Anaesthetists
CRQ	Constructed response questions

**Keywords:** Regional Anaesthesia, Sonoanatomy

## Study Summary

Title	URAISE: Ultrasound Regional Anaesthesia Interpretation Skill Evaluation
Design	Prospective study based on psychometric principles
Aims	To generate a validated test of ultrasound guided regional anaesthesia that can be used to differentiate reliably between users of different skill levels.
Outcomes	
Primary outcome:
 
Development of a validated, reliable and defensible tool to test ultrasound guided regional anaesthesia image interpretation skills.
 
Secondary outcomes:
 
Development of a validated, reliable and defensible assessment tool assessing anatomical, clinical knowledge and the performance of ultrasound guided regional anaesthesia:
 
Assessment of anatomical knowledge relevant to performing a local anaesthetic injection around peripheral nerves
 
Assessment of clinical knowledge relevant to regional anaesthesia required to perform a local anaesthetic injection around peripheral nerves
 
Assessment of knowledge relating to the performance of an ultrasound-guided local anaesthetic injection around peripheral nerve

Population	UK anaesthetic trainees and consultants
Eligibility	Participants must be registered in an approved UK anaesthetic training programme, or anaesthetic consultants on the GMC register
Duration	12 months

## 1. Introduction

### 1.1 Background

There is a drive for trainee anaesthetists to be competent in a number of common ultrasound guided blocks and proficiency is considered an important part of the anaesthetic curriculum laid out by the RCoA. Ultrasound improves the safety, efficacy and efficiency of peripheral nerve blocks. It is now the accepted standard of practice in most institutions. However, one challenge for trainers and trainees is that there is a lack of simple, readily available, evidence-based and validated methods to assess the anaesthetists' ability to identify structures using ultrasound. The development of a validated tool to evaluate proficiency in ultrasound-guided regional anaesthesia (UGRA) interpretation would improve the uniformity and consistency of assessment in the UK.

Validated tools for assessment of ultrasound may be even more valuable with the recognised advantages and increased use of regional anaesthetic techniques during the COVID-19 pandemic. Possible advantages to anaesthetists and hospitals include reduced risk of transmission to staff, and preservation of drugs and personal protective equipment required during critical care of COVID-19 patients. These patients may also benefit from avoiding the further cardiorespiratory strain of undergoing a general anaesthetic. All patients may also experience improved postoperative pain relief (thereby also minimising direct contact with care givers), reduced time in recovery and earlier hospital discharge.

**Legal defensibility** is a concept that is central to any assessment tool. There needs to be confidence in the processes used to construct the assessment tool and that the outcomes of the test reflect the participant's ability. The application of rigorous **psychometric principles** is essential to achieving the high standard of **validity** and **reliability** of an assessment required by educational institutions. Anaesthetists seeking certification that is not based on a validated assessment method could give rise to the question of ethical injustice and possibly expose an organisation to legal challenges. On the other hand, anaesthetists that are inappropriately certified may risk patient safety.

The assessment tool must measure what it is supposed to measure. Firstly, **face validity** will be ensured by our participants judging the questions as easy to understand and the ultrasound video quality as representative of clinical practice. The **content validity** of the assessment tool will be verified by a panel of experts who will be asked to assess its relevance to regional anaesthesia by matching it to the RCoA curriculum. Next, the **construct validity** of the assessment will be evidenced by anaesthetists with more regional anaesthesia experience achieving higher ultrasound interpretation scores. The stages of training in our assessment tool will include consultants and will also be based on the new 2021 RCoA curriculum that is

divided into Stage 1 (CT1-3), Stage 2 (ST4-5) and Stage 3 (ST6-ST7) in a spiral curriculum that is both competency and time-based. This is also a proxy outcome measure in that advancement through these competency-based stages of training already include forms of assessment of proficiency in UGRA. Demographic information will be gathered from the participants to demonstrate their prior regional anaesthesia experience. This will factor in additional courses, qualifications and fellowships in relevant areas to account for inconsistencies in clinical exposure to ultrasound throughout training and as a practising anaesthetist (specifically, training level, courses attended, regional anaesthesia fellowships completed, and ultrasound-based fellowships completed).

Consistency of measurement or **reliability** is essential in the assessment tool. **Cronbach's alpha method** is commonly used to assess internal consistency reliability. We will use also use a “**split-half**” method of comparison in the final version of the test wherein the performance of the same participant in the first half is compared to their performance in the second half. The optimal test length is a balance. Using more test items produces more measurements of the construct and therefore result in higher reliability. This must be set against potential cognitive fatigue and participant drop out with longer test times. Statistical analysis of the pilot testing will allow items with higher discrimination to be kept in the final version of the test and lower discrimination, or lower measurement value, to be removed. Inter-rater or marker variability can be minimised by a system of automatic computer marking. However, the marking will also be corroborated by manual checking by investigators blinded to the participant’s training level and experience.

Several studies have conducted psychometric evaluations of assessment tools for the development of regional anaesthesia knowledge and skills. These include measuring hand-motion analysis, visuospatial and psychomotor screening, checklists and global rating scales. In particular, Woodworth *et al* showed the validity and reliability of a 47-item multiple-choice online test of ultrasound interpretation skills for regional anaesthesia that can be used as an assessment of competence milestone in anaesthesia training for a training programme in the USA. There has not been a study to create such an assessment tool in the UK, where the training programme differs from that in the USA. The UK has a seven year specialist anaesthetic training programme compared to the American four year residency in anaesthesiology. There is evidence that “constructed response questions” (CRQs) with free text answers require a higher degree of understanding and are considered higher on Bloom’s taxonomy (knows, comprehends, applies, analyses, synthesises, evaluates) in terms of the complexity of skills demonstrated by the learner. This is also in line with the changing curriculum of the RCoA that has recently moved towards using CRQs in their Final Fellowship of the Royal College of Anaesthetists (FRCA) examinations. These CRQs challenge trainees to

apply, justify or compare information to arrive at solutions to clinical questions, thereby better reflecting daily clinical practice. We therefore aim to create a well-validated assessment tool that uses CRQs to assess ultrasound interpretation skills, which is grounded in the psychometric principles of validity, reliability and defensibility.

## 2. Study Objectives

The primary objective of the study is the development of a validated, reliable and defensible assessment tool to test ultrasound-guided regional anaesthesia image interpretation skills.

The secondary objectives are development a validated, reliable and defensible assessment tool assessing anatomical and clinical knowledge relevant to regional anaesthesia; as well as assessing knowledge pertaining to the performance of ultrasound guided regional anaesthesia:

- Assessment of anatomical knowledge relevant to performing a local anaesthetic injection around peripheral nerves
- Assessment of clinical regional anaesthesia knowledge relevant to performing a local anaesthetic injection around peripheral nerves
- Assessment of the performance of an ultrasound-guided local anaesthetic injection around peripheral nerve

This will support training and assessment in UGRA by UK anaesthetists by enabling trainers to track educational progress. This in turn will support performance of UGRA, improving patient experience, enhancing patient safety by reducing complications associated with these blocks, and increasing the pool of skilled UGRA practitioners.

### 3. Study Design

This is a prospective, multi-centre study leading to the identification of a validated, reliable and defensible assessment tool for assessing UGRA image interpretation.

Study population	Anaesthetists in the UK
Inclusion	Registered in an approved UK anaesthetic training programme Anaesthetic consultants on the GMC register
Exclusion(s)	Staff grade, associate specialist and specialty doctors not enrolled in a UK anaesthetic training programme
Sample size	Pilot phase: 35-50      Study phase: 250
Duration	12 months
Study centres	Imperial College Healthcare NHS Trust, London  Royal Gwent Hospital, Aneurin Bevan University Health Board, Wales  Southern Health and Social Care Trust, Northern Ireland, UK  Belfast Health and Social Care Trust, Northern Ireland, UK  NHS Greater Glasgow & Clyde, Scotland, UK  Guy's & St Thomas NHS Foundation Trust, London, UK  Frimley Health NHS Foundation Trust, UK
Primary outcome	A validated, reliable and defensible assessment tool to test ultrasound-guided regional anaesthesia image interpretation skills
Secondary outcome(s)	The secondary outcomes are development a validated, reliable and defensible assessment tool assessing anatomical, clinical knowledge and the performance of ultrasound guided regional anaesthesia: 

• Assessment of anatomical knowledge relevant to performing a local anaesthetic injection around peripheral nerves

• Assessment of clinical regional anaesthesia knowledge relevant to performing a local anaesthetic injection around peripheral nerves

• Assessment of the performance of an ultrasound-guided local anaesthetic injection around peripheral nerve

This study will have 5 Phases:

### 3.1 Phase 1 – Nerve block identification

A panel of academic experts in regional anaesthesia will extensively review published evidence from UGRA international consensus guidelines. This first step will determine which UGRA nerve blocks are relevant to clinical practice and anaesthetic training in the UK, in particular their relevance to the new RCoA curriculum. The anatomical and clinical knowledge that is relevant to these nerve blocks will also be listed.

### 3.2 Phase 2 – Content and question generation

A panel of experts in regional anaesthesia will review UGRA nerve blocks and their relevant anatomical structures. The anatomical structures that must be identified on ultrasound for the safe and effective performance of these blocks will be agreed upon using the Delphi method. It will help determine whether these structures are essential for block performance, desirable, expert or not relevant. The experts in the panel will be defined by their experience – they will all be recognised nationally or internationally for their involvement in regional anaesthesia societies and publications. This information will be collated by the Primary and co-investigators to generate a pilot test of UGRA interpretation content and questions.

### 3.3 Phase 3 – Preliminary testing

The pilot test will be administered by local investigators via a computer-based application (<https://www.classmarker.com/>) to 35-50 trainees and consultants, recruited by email and flyers sent to schools of anaesthesia across the UK. The cohorts will include an equal number of trainees and consultants of varying experience, based on the new RCOA curriculum and the extent of their regional experience (stage 1 (CT1-3); stage 2 (ST4-5); stage 3 (ST6-7); stage 3 + regional fellowship trained; consultant; consultant with special interest in regional; consultant + regional fellowship trained). The pilot test will contain short video clips and images of ultrasound guided regional anaesthesia with questions in a constructed response question (CRQ) format to identify relevant structures, anatomy and clinical knowledge. It is important to recognise that due to the change in the RCoA curriculum, some participants will be familiar with the CRQ format while others might be more familiar with MCQ-based format, or other forms of assessment question. Participants in the pilot and main study will be provided with sample questions and answers prior to the test to familiarise themselves with the question format.

Face validity of the test will also be assessed by asking participants to comment on the ease of understanding and to identify terms that appear ambiguous. Participants will be able to comment in a text box after each item in the questionnaire. They will also be asked to comment on how they would improve the test and any relevant anatomy or clinical

knowledge missing from the questions. The format of the test will be amended based on the comments.

A difficulty index of each item will be calculated by dividing the number of correct responses by the total number of responses, as detailed in Abubakar *et al*'s study, and thus a higher value suggests a question is easier to answer. Any item with a difficulty index of < 50% will be considered too difficult to answer by the respondents and will be considered for removal. This will be compared to the information gathered from the panel of experts on test items, for example whether the anatomical structure is essential, desirable, expert or not relevant to the specific ultrasound guided nerve block.

One important step in establishing construct validity is to use the pilot study to identify how well the answers for each test item discriminate between the participant's level of ultrasound experience. Differences in ultrasound interpretation skills between study groups will be analysed using one-way analysis of variance (ANOVA)/Rasch modelling. Items that discriminate well will be retained and those that discriminate poorly will be removed from the main test.

Reliability of the test will be improved by presenting the pilot test items in a random order to minimise any effect of cognitive fatigue diminishing performance on subsequent items. The average time taken for participants to complete each item in the pilot test will also be recorded to guide the optimal final study test length. It is important to balance the maximum number of test items whilst minimising the risk of cognitive fatigue and participant drop out. While the pilot test will necessarily have more items than the final test, pilot test participants will be asked to comment on the point at which they felt fatigued to guide this balance. It will also be important to understand whether level of regional anaesthesia experience affects fatigability.

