# 7. Statistics and Data Analysis

## 7.1 Sample Size Calculation

Sample size for the definitive data capture stage, 'Phase 5 – Psychometric main study testing', will be calculated using a power calculation based on data obtained in the pilot work during 'Phase 3 – Preliminary testing'. For example, internal reliability of the item responses is to be assessed using Cronbach's alpha, an alpha value of 0.70 being considered adequate. With 250 participants completing a 50-item questionnaire it would be possible to show that Cronbach's alpha is significantly higher than 0.6 if the true value is 0.7 i.e. there is

a greater than 85% chance (power) that the 95% confidence interval for Cronbach's alpha will exceed 0.6 and include 0.7.

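### The pilot's only stated measure of fatigue is participants' comments; randomising item order per participant and storing position would let their answers be used as well

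*Combined protocol and SAP*

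**What the plan says.** Section 1.1 presents test length as a balance: more items raise reliability, but a longer test risks fatigue and drop-out. Section 3.3 gives the pilot the task of settling that balance, through these provisions:

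- Reliability is to be improved by "presenting the pilot test items in a random order to minimise any effect of cognitive fatigue diminishing performance on subsequent items". The text does not say whether the order is drawn once or separately for each participant, or whether each item's position is retained.
- The average time per item is "recorded to guide the optimal final study test length".
- On fatigue itself, "pilot test participants will be asked to comment on the point at which they felt fatigued to guide this balance".
- On experience: "It will also be important to understand whether level of regional anaesthesia experience affects fatigability". No measure, model or comparison follows.

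The pilot test goes "to 35-50 trainees and consultants, recruited by email and flyers sent to schools of anaesthesia across the UK", in seven experience groups. Its length is not given, except that "the pilot test will necessarily have more items than the final test".

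The analyses in section 7.3 are the difficulty index, the content validity index, ANOVA/Rasch modelling, Cronbach's alpha and a split-test. None uses item position. The comparison of first and second halves in section 3.5 belongs to the main study, after length has been fixed, and its stated purpose is internal consistency.

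**The concern.** What matters for test length is how far performance deteriorates as the test goes on. A comment on when someone felt tired is a proxy: a participant can feel tired and still answer well, or lose accuracy without noticing. Relying on it could shorten the test needlessly or leave a real loss undetected. An average time per item, pooled over positions, does not show fatigue either.

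The silence about the random order has a second consequence. If each participant receives a different order, any late-test loss is spread over all items. If everyone receives the same random order, the loss falls on whichever items come last, and these look harder than they are. That error would enter the below-50% difficulty rule (grounds to consider removal in 3.3, sufficient to exclude in 7.3). It would also enter the balancing of the two halves of the main test, which 3.5 bases on pilot difficulty.

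The experience question bears on construct validity. If less experienced participants lost more accuracy late in the test, part of the experience gradient in Phase 5 could reflect that loss.

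**Working it through.** **The plan's own figure.** The only power statement, in 7.1, concerns Cronbach's alpha: "a greater than 85% chance (power) that the 95% confidence interval for Cronbach's alpha will exceed 0.6 and include 0.7", with 250 participants, 50 items and a true alpha of 0.7.

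- Feldt's F distribution (249 and 249 × 49 = 12,201 degrees of freedom) gives an 89.4% chance that the lower limit exceeds 0.6, and 86.9% that the interval also includes 0.7.
- Bonett's approximation: SE = √[2 × 50/(49 × 248)] = 0.0907; ln(0.4/0.3) = 0.2877; 0.2877/0.0907 − 1.96 = 1.21; power 88.7%.

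The stated figure reproduces. The present point does not depend on it.

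**Inputs.** From 3.3: 35-50 participants in seven groups, so about 5-7 per group. Assumed, because the documents do not say: 60-100 pilot items and about 65-70% correct overall.

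**Overall fall, by formula (separate order per participant).** With position scaled from 0 to 1 its variance is 1/12, so the SE of the linear first-to-last fall is √[12p(1−p)/(nk)]. At p = 0.65 the numerator is 12 × 0.2275 = 2.73.

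- n = 35, k = 60: √(2.73/2100) = 0.036. Detectable with 80% power: 2.8 × 3.6 ≈ 10 points.
- n = 50, k = 80: √(2.73/4000) = 0.026. Detectable: 2.8 × 2.6 ≈ 7 points.

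**Experience difference, by formula.** Comparing two equal halves of the sample doubles the SE, so about 15-20 points is detectable.

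**Simulation.** Logistic responses, ability SD 0.8, item SD 1.0, about 66-70% correct, 600 runs per setting. Entries are falls detectable with 80% power (2.8 × simulated SE), in percentage points.

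| Participants | Items | Overall fall | Difference in fall, lowest v highest experience group |
|---|---|---|---|
| 35 | 60 | 8.5 | 25.9 |
| 35 | 80 | 7.6 | 21.3 |
| 35 | 100 | 6.2 | 21.0 |
| 50 | 60 | 7.3 | 21.3 |
| 50 | 80 | 6.6 | 19.6 |
| 50 | 100 | 5.5 | 18.1 |

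Power is 90-100% for an overall fall of about 10 points and 36-70% for about 5 points. For a 10-point difference between the extreme experience groups it is 19-38%.

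**One shared order.** With no fatigue at all, a simple test of score against position at 80 items rejects in 45% of runs (n = 35) and 58% (n = 50), because chance differences in item difficulty line up with position.

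**Effect on the difficulty rule, as an illustration.** With 40 respondents an item is below 50% when 19 or fewer are correct. The binomial probability of this is 21% at a true 55%, and 68% if accuracy is lowered to 45%. The second figure assumes a shared order, a 10-point fall and an item in last place. None of these comes from the documents.

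**Could a fixed fall set the length?** Suppose the true fall is 10 points and linear. The 95% interval is 10 ± 1.96 × 2.6 = 4.9 to 15.1 at best, and 10 ± 1.96 × 3.6 = 2.9 to 17.1 at worst. In the worst case a 5-point threshold is reached anywhere from 5/17.1 = 29% of the way through the test to not at all.

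**The case against.** **A reader might infer that test length rests on recollection alone.** The documents do not support this. Item times also guide length, items are cut on discrimination and difficulty, and 3.3 offers a comment box after each item, so fatigue could be reported during the test. Nor do they say that the experience effect will be judged from comments; they give no method. What stands is that comments are the only fatigue measure named.

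**A reader might infer that the randomised order already permits the better analysis.** It does so only if the order differs between participants and position is stored. Separate orders are arguably the natural reading, since the stated aim is to protect later items, but neither condition is written down.

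**A reader might take the slope on position as an unbiased estimate of fatigue.** It is a net effect. Sections 3.3 and 7.2.2 say that some participants will be less used to the constructed-response format, so practice could offset fatigue and a flat slope could hide it. Participants who tire and stop would also leave the late positions to those less affected.

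**Comments have their own value.** The balance in 3.3 includes drop-out, and accuracy does not measure willingness to continue. This stands, and the comments should be kept.

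**The main study would show a late drop anyway.** Its difficulty-balanced halves in 250 participants might well do so, but only after length has been fixed.

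**The pilot is too small.** This is correct for the experience question and for locating where a decline begins. It is not correct for an overall fall of about 6-10 points or more.

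**Conclusion.** The point holds in a limited form. Fatigue has no performance-based measure in the pilot, the experience question has no method, and the plan is silent on two details that decide whether answers could be used: a separate order for each participant, and stored position. If these are secured, the planned pilot can detect an overall first-to-last fall of about 6-10 points, and an experience difference of only about 15-26 points, assuming 60-100 items and about 65-70% correct. The experience analysis is therefore exploratory, and the suggestion that stamina explains part of the Phase 5 gradient remains conjecture.

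The figures do not support a hard length rule such as a 5-point fall, and a single linear slope cannot show where a decline starts. The harm to the difficulty rule is conditional on a shared order, which the documents neither state nor exclude. This is a pilot design matter and not a fault in the primary analysis, but it should be settled before the pilot opens: a shared order or unrecorded positions cannot be put right afterwards.

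**What to change.** In section 3.3:

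1. State that item order is randomised separately for each pilot participant, and that the serial position and response time of every item are stored.
2. Prespecify a mixed logistic model of correct/incorrect on position, with participant and item effects. Report the estimated first-to-last change with its 95% confidence interval, described as a net position effect (fatigue less practice). Add a binned or flexible position term as a check on linearity.
3. Use this estimate beside the comments and item times when setting the final length, without a fixed cut-off.
4. Include experience-by-position as an exploratory term, reported as an estimate with its interval.

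Add the model to the list in section 7.3. The cost is a platform setting and one additional model on data that the pilot will largely collect anyway. No extra participants are needed.
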